#### **4.3.2 Protocol Deviations**

Important Protocol Deviations (IPD) will be summarized by treatment group within each study part, pooled treatment groups, and over all subjects combined for the Full Analysis Set. Important Protocol Deviations are identified by the Sponsor and are defined in the ICH guideline *Structure and Content of Clinical Study Reports – Questions and Answers (E3[R1], 2013)* as a subset of protocol deviations that might significantly affect the completeness, accuracy, and/or reliability of the study data or that might significantly affect a subject's rights, safety, or well-being.

All IPDs will be determined and appropriately categorized prior to database lock and prior to breaking the blind of the treatment group assignments. The number and percentage of subjects with any IPDs as well as the number and percentage of subjects with IPDs within each category will be presented. Important protocol deviations will be included in a listing.

### **4.4 Efficacy Evaluation**

#### **4.4.1 Datasets Analyzed**

All efficacy summaries will be based on the Full Analysis Set. A data listing of subjects excluded from the Full Analysis Set, to include the reason for exclusion, will be presented.

#### **4.4.2 Demographic and Other Baseline Characteristics**

Demographic variables including age, sex, ethnicity and race will be summarized by treatment group within each study part, pooled treatment group, and over all subjects combined for the Safety Analysis Set, Full Analysis Set, and PK Set (to include applicable EP262 treatment groups only).

Age will be summarized using descriptive statistics. Sex, ethnicity, and race will be summarized with the number and percentage of subjects in each parameter category.

Baseline characteristics include medical history, height, weight, and body mass index (BMI), and disease characteristics. Body mass index will be calculated as: weight (kg) / [height (cm) / 100]. Height, weight, and BMI at baseline will be summarized using descriptive statistics.

Baseline disease characteristics include time since CSU diagnosis (as reported on the Disease History eCRF), history of angioedema, baseline [REDACTED] score, baseline [REDACTED] score and disease severity category, baseline [REDACTED] baseline total [REDACTED] (kU/L), prior use of omalizumab, prior CSU therapy, and best response to prior CSU therapy. Presence

of baseline angioedema will be determined by a subject's response to the medical history question "presence of angioedema."

Time since CSU diagnosis (in years) is calculated as the informed consent date – the date of diagnosis divided by 365.25. Subjects with partial dates reported for the date of diagnosis will have time (years) calculated utilizing the available date information reported. Time will be calculated using the available date information relative to informed consent. If only year is present, time is calculated relative to the informed consent year. If year and month are present, time is calculated relative to informed consent year and month. Time since CSU diagnosis will be summarized using descriptive statistics.

The remaining variables will be summarized by the number and percentage of subjects within each category. Best response to prior CSU therapy will be based on all reported individual prior CSU therapies to determine the overall best response reported, where a Complete Response would be the best possible response and No Response is the worst possible response. Unknown responses will take the lowest priority in the evaluation.

Baseline characteristics will be summarized by treatment group within each study part, pooled treatment groups, and over all subjects combined for the Safety Analysis Set, Full Analysis Set, and PK Set (to include applicable EP262 treatment groups only).

Prior CSU therapies will be coded using the World Health Organization (WHO) Drug Global B3, version March 1, 2023. Medications entered on the eCRF will be mapped to Anatomical Therapeutic Chemical (ATC) drug class (level 2) and preferred name. The number and percentage of subjects receiving any prior CSU therapy will be summarized by treatment group, as will the number and percentage receiving any medication by ATC drug class and preferred name. Subjects reporting use of more than one medication at each level of summarization (any medication received, ATC class, and preferred name) will be counted only once. ATC class terms will be displayed by descending order of incidence, as will preferred names within each ATC class.

Medical history conditions will be mapped to preferred terms and system organ classes using the Medical Dictionary for Regulatory Activities (MedDRA, version 26.0). Frequency counts and percentages to summarize subjects reporting medical history by system organ class and preferred term will be presented.

A summary of background therapy medications (as described in [Section 3.3.1.1](#)) will be provided. Background therapies include CSU therapies reported on the Prior CSU Therapy eCRF with an ongoing end date or an end date that continues through first dose of study drug). The number and percentage of subjects reporting a background H1AH will be determined as any medication reported in the ATC level 2 of "ANTIHISTAMINES FOR SYSTEMIC USE."

The number and percentage of subjects receiving any background therapy will be summarized by treatment group, as will the number and percentage receiving any H1AH background medication by preferred name. In addition, a summary of any "other" background therapy medications will also be provided and summarized by preferred name. The summary of "other" background therapy medications will include

any CSU therapies ongoing at the initiation of study treatment that are not captured in the ATC level 2 of “ANTIHISTAMINES FOR SYSTEMIC USE.” A listing of qualifying background therapy medications will be provided.

#### **4.4.3 Primary Efficacy Endpoint Analysis Methods**

The core attributes of the estimand for the analysis of the primary endpoint are as follows:

- **Population:** The primary endpoint will be analyzed among all subjects in the Full Analysis Set. The population is further defined via the inclusion and exclusion criteria as part of the protocol. A key aspect of eligibility is that subjects must have moderate-to-severe disease activity in CSU at baseline, defined as a UAS7 of at least 16.
- **Treatment Conditions:** Participants are randomized in a 1:1:1 ratio to receive 50 mg of EP262, 150 mg of EP262, or placebo in Part 1 and randomized in a 3:1 ratio to receive 25 mg of EP262 or placebo in Part 2, to receive once daily drug administration during a 6-week Double-Blind Treatment Period. The primary analysis will compare each active EP262 group to Placebo at Week 6.
- **Endpoint:** The primary efficacy endpoint is the change from baseline in UAS7 at Visit 4 (Week 6).
- **Summary Measure:** The difference in model-adjusted means between each EP262 treatment group and Placebo in the change from baseline weekly UAS7 value.
- **Handling of Intercurrent Events (ICEs):** Potential ICEs that a subject may experience on study include:
  - Premature discontinuation from study drug as described in Section 8.6.1 of the clinical study protocol.
  - Use of prohibited and/or rescue medication as described in Section 8.2 (Subject Exclusion Criteria) of the clinical study protocol and [Section 3.3.1.2](#) of the SAP, respectively.

Subjects who experience an ICE prior to Week 6 will have data collection handled by the treatment policy strategy, consistent with the intent-to-treat principle.

Placebo subjects in Part 1 and Part 2 (if available) will be pooled for the treatment comparison analysis. The null hypothesis to be tested is that there is no difference in the mean change from baseline between EP262 (each dose level) and Placebo:

$$H_0: \mu_A = \mu_P;$$

Where  $\mu_A$  and  $\mu_P$  represent the mean change from baseline values for EP262 and Placebo, respectively. The alternate hypothesis to be tested is that the treatment group means differ:

$$H_1: \mu_A \neq \mu_P;$$

[figure not shown]
Treatment groups will be compared at Week 6 using a mixed-effects model for repeated measures (MMRM). The model will include fixed effects for treatment group, week (visit), treatment group by week interaction, the stratification factor of prior omalizumab use (randomization strata), and the UAS7 baseline value as a covariate. The model will include data at all post-baseline visits scheduled for collection in the Double-Blind Treatment Period and the comparison will be made using the treatment group by week interaction term for the Week 6 assessment. The unstructured covariance matrix will be used; in the event the computational algorithm fails to converge, the following structures will be executed: heterogeneous Toeplitz, Toeplitz, heterogeneous First-Order Autoregressive [AR(1)], AR(1), heterogeneous compound symmetry (CS), and CS. The covariance structure converging to the best fit, as determined by Akaike's information criterion (AIC), will be used. The Kenward and Roger method will be used to calculate the denominator degrees of freedom for the test of fixed effects. The model uses a likelihood-based estimation method that assumes data to be missing at random to account for subjects who discontinue the study prior to Week 6.

[figure not shown]
Statistical testing will be performed as a 2-sided test with a statistical significance level of 0.10 (alpha = 0.10). Estimates of least-square (LS) means, standard error, and 90% CIs will be presented by treatment group. In addition, the LS mean difference (LSMD) of each comparison between EP262 and placebo, the standard error of the difference, and 90% CI of the difference will be presented. Each pairwise comparison between EP262 and placebo will be conducted at a 10% level, with no adjustment for multiplicity.

[figure not shown]

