16.8.1. Primary Efficacy Analysis

The UAS7 will be analyzed using a mixed effects model for repeated measures based on the data from each week up to Week 6. The model will include treatment, week, and treatment by week interaction as fixed effects. Additional model covariates will include baseline UAS7 score and randomization strata. The treatment effect will be the contrast between EP262 and placebo least-squares (LS) means.

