## 3.4 Efficacy and Safety Variables

### 3.4.1 Efficacy Variables

#### 3.4.1.1 Primary Efficacy Variable

The primary efficacy endpoint is change from baseline to Visit 4 (Week 6) in the sum of the daily UAS over a 7-day period (UAS7).

The UAS is a CSU-specific, 24-hour self-evaluation, patient-reported outcome measure ([Zuberbier 2022](#)). It is based on the assessment of key CSU symptoms: intensity of itch and number of wheals. The UAS scale for both itch (Itch Severity Score; ISS) and wheal assessment (Hive Severity Score; HSS) are recorded as a score from 0 to 3 (Total = 0 to 6), with 0 representing no itch/hives to 3 representing intense itch/hives (i.e., Itch – interferes with normal daily activity or sleep; Hives – More than 50 wheals). Daily UAS scores are summed over 7 consecutive days to derive the UAS7. The UAS7 scores range from 0 to 42, with higher scores indicating greater disease severity. Well-controlled urticaria (minimal disease activity) is defined as a UAS7 score  $\leq 6$ . The minimally important difference (MID) for UAS7 is considered a reduction in baseline of  $\geq 10$  ([Mathias 2012](#)).

Subjects will be instructed to complete the UAS daily, in the morning before dosing (as applicable), and at approximately the same time of day, beginning at the Screening Visit to the Safety Follow-Up Visit. The questionnaire will be completed during the Screening Visit. For all other days that coincide with a study visit (for Visit 2 and beyond), the UAS is to be completed in the morning before the study visit.

The UAS scores from Day -7 through Day -1 will be summed to determine subject eligibility for continued participation regarding disease activity. An example of the UAS is included in Appendix C of the clinical study protocol.

For UAS, a weekly score will be computed as the sum of the daily UAS over the 7 days prior to or on the timepoint of interest. The UAS7 will be derived for the following analysis visits: Baseline, Week 1, Week 2, Week 3, Week 4, Week 5, and Week 6 of the Double-Blind Treatment Period. Analysis visits will also be derived for Week 7, Week 8, Week 9 and Week 10 of the Safety Follow-Up Period. The following visit window considerations will be applied:

- The UAS scores from Day -6 through Day 1 will be summed to serve as the baseline UAS7 score.

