#### ***4.4.5 Exploratory Endpoint Analysis Methods***

#### ***4.4.6 Statistical/Analytical Issues***

##### ***4.4.6.1 Adjustments for Covariates***

The MMRM to compare treatment groups for the primary endpoint will include a covariate adjustment for the baseline UAS7 value.

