#### **4.6 Determination of Sample Size**

The study will enroll approximately 154 subjects.

In Part 1, approximately 114 subjects will be randomized in a 1:1:1 ratio to receive 50 mg of EP262, 150 mg of EP262, or placebo.

In Part 2, approximately 40 subjects will be randomized in a 3:1 ratio to receive 25 mg of EP262 or placebo.

Overall, approximately 30, 38, 38, and 48 subjects will be randomized to receive 25 mg EP262, 50 mg EP262, 150 mg EP262, and placebo, respectively, across both parts of the study.

For Part 1, a sample size of 34 subjects per treatment group will provide 80% power to detect an 8-point difference in the UAS7 change from baseline at Visit 4 (Week 6), assuming a standard deviation of 13 points, and a 2-sided alpha of 10%.

For Part 2, a sample size of 27 subjects receiving 25 mg of EP262 and 43 subjects receiving placebo pooled from both parts of the study will provide 80% power to detect an 8-point difference in the UAS7 change from baseline at Visit 4 (Week 6) between EP262 25 mg and placebo, with the same assumption of 13-point standard deviation and 2-sided alpha of 10%.

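### The primary MMRM fits one baseline UAS7 slope to Weeks 1 to 6; a baseline-by-week term would cheaply protect precision at Week 6

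*SAP*

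**What the plan says.** SAP 4.4.3 fits treatment, week and their interaction, then the omalizumab stratum and baseline UAS7; the relevant words are "treatment group by week interaction, the stratification factor of prior omalizumab use (randomization strata), and the UAS7 baseline value as a covariate". Protocol 16.8.1 agrees: "Additional model covariates will include baseline UAS7 score and randomization strata". SAP 4.4.6.1 says only that the model "will include a covariate adjustment for the baseline UAS7 value", and SAP 4.4.6.2 restates the model in the same way. Neither document adds a baseline-by-week term.

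SAP 3.4.1.1 derives UAS7 at "Baseline, Week 1, Week 2, Week 3, Week 4, Week 5, and Week 6 of the Double-Blind Treatment Period", so six post-baseline weeks enter the model. On the covariance, SAP 4.4.3 says: "The unstructured covariance matrix will be used". Simpler structures are used only if that fit does not converge.

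**The concern.** The Week 6 difference between an EP262 arm and placebo is the difference in mean change minus the baseline slope times the difference in mean baseline. With a main effect only, that slope is shared by all six weeks. Generalised least squares gives most weight to the weeks with the least residual variance, which tend to be the early ones.

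The design makes drift plausible. Week 1 follows directly on the baseline window, whereas Week 6 is five weeks later. Baseline is confined to 16 to 42 by the entry criterion and the scale, while the SD of the Week 6 change is assumed to be 13.

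If the slope of change on baseline steepens over time, Week 6 receives too flat a correction. At stake are some precision and some of the correction for baseline imbalance at the primary time point, in arms of 27 to 43 evaluable subjects.

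**Working it through.** **1. The plan's own figure.** SAP 4.6 states that "a sample size of 34 subjects per treatment group will provide 80% power to detect an 8-point difference", with SD 13 and two-sided alpha 0.10.
- n per arm = 2 × (1.645 + 0.842)² × 13² / 8² = 32.7, so 33.
- With 34 per arm the SE is 13 × √(2/34) = 3.15, and power is Φ(8/3.15 − 1.645) = 81.4% (80.7% by noncentral t).
- With 27 vs 43 the SE is 13 × √(1/27 + 1/43) = 3.19, and power is 80.5% (79.9% by t).

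The figure reproduces. It uses the unadjusted SD, so it does not rely on baseline adjustment.

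**2. Formulas.** These assume complete data and a separate mean for each treatment and week.
- Slope of change on baseline in week k: s_k = r_k × SD_k / SD_b − 1, where r_k is the correlation of week-k UAS7 with baseline.
- Common slope: b = 1′S⁻¹s / 1′S⁻¹1, where S is the unstructured residual covariance including the misfit, solved by iteration.
- Week 6 residual variance = (variance with its own slope) + (s_6 − b)² × SD_b².

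**3. Inputs.** SD_b, SD_k, r_k and the residual correlations are not in the documents. All are assumed below. Weekly SDs and correlations run linearly from Week 1 to Week 6, and results are scaled so that the unadjusted Week 6 change SD is 13.

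**4. One case in full.** SD_b 8, weekly SD 9 to 12, r 0.75 to 0.30, residual correlation 0.7 between any two weeks.
- s_6 = 0.30 × 12/8 − 1 = −0.55, and the common slope is b = −0.053.
- Unadjusted change SD = √(144 + 64 − 57.6) = 12.26, so the scale factor is 13/12.26 = 1.06.
- Variance with the Week 6 slope = 144 × (1 − 0.09) = 131.0. Misfit adds 0.497² × 64 = 15.8.
- The ratio is 146.8/131.0 = 1.12. Scaled SDs are 12.13 and 12.85.

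**5. Six patterns at that residual correlation.** Power is by noncentral t at 34 per arm.

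| SD_b; weekly SD; r | s_1 | s_6 | b | SD, own slope / common | Variance ratio | Power, own slope / common |
|---|---|---|---|---|---|---|
| 8; 9–12; 0.75–0.30 | −0.16 | −0.55 | −0.05 | 12.13 / 12.85 | 1.12 | 85.2% / 81.5% |
| 7; 8–12; 0.80–0.30 | −0.09 | −0.49 | +0.03 | 12.46 / 13.06 | 1.10 | 83.5% / 80.4% |
| 7; 9–13; 0.70–0.35 | −0.10 | −0.35 | −0.03 | 12.74 / 12.96 | 1.03 | 82.0% / 80.9% |
| 8; flat 12; 0.60–0.30 | −0.10 | −0.55 | −0.18 | 12.13 / 12.53 | 1.07 | 85.2% / 83.2% |
| 7; 11–12; 0.55–0.30 | −0.14 | −0.49 | −0.17 | 12.46 / 12.69 | 1.04 | 83.5% / 82.3% |
| 8; 10–12; 0.65–0.45 | −0.19 | −0.32 | −0.18 | 12.63 / 12.71 | 1.01 | 82.6% / 82.2% |

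Across 48 scenarios with other residual correlations, the common slope was always nearer the Week 1 than the Week 6 slope. The excess variance ran from 0.5% to 16%. The maximum was the first row with residual correlation 0.8 (power 85.2% against 80.4%). Single-slope power was 79.8% to 84.1% at 34 per arm and 79.0% to 83.4% at 27 vs 43.

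**6. Simulated MMRM.** 154 subjects, 10% monotone dropout, 400 runs in each of six settings.
- True slopes −0.16 (Week 1) and −0.55 (Week 6): the fitted common slope averaged −0.06 to −0.19. The model SE was 2.82 to 2.85 with one slope and 2.70 to 2.74 with the interaction, which is 6% to 11% of variance setting by setting.
- True slopes −0.10 and −0.35: 1% to 3% of variance.
- Mean estimates lay between −7.8 and −8.1 for a true −8.

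A separate set of simulations used 27/34/34/43 subjects. It gave variance ratios of 1.014, 1.033, 1.100, 1.031 and 0.997, and 0.994 when the slopes were equal.

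**7. Imbalance left uncorrected.** With SD_b 8 and 34 per arm, the chance difference in mean baseline has SD 8 × √(2/34) = 1.94 points. The simulated slope errors of 0.36 to 0.49 leave a component with SD 0.7 to 0.95 points, against the 8-point target.

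**The case against.** The strongest reply is that nothing here is an error. A main-effect covariate is a legitimate specification, and the SAP carries out the protocol's model faithfully. Any figure for the loss comes from inputs that a reviewer chose. Rapid onset of action, which Protocol 5.2 anticipates, and the entry floor of 16 would both tend to lower the Week 1 correlation with baseline and so reduce the drift. Where drift is small, the gain is about 1% of variance or nothing. The baseline adjustment is itself modest: even with week-specific slopes the SD only falls from 13 to between 12.1 and 12.7.

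All of that stands, and it rules out three stronger readings.

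- **That Week 6 will in fact be adjusted with roughly the Week 1 slope.** The documents contain no weekly variances or correlations from which this could be shown.
- **That the primary estimate is biased or the test invalid.** Under randomisation the Week 6 contrast is unbiased whatever slope is used. The unstructured Week 6 variance absorbs the misfit, so type I error is not inflated and the 90% CI holds.
- **That the 80% power claim fails.** It was computed at SD 13 without adjustment. In the worst scenarios the single-slope SD exceeds 13 only slightly (13.17, power 79.8%).

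One qualification applies. Pooled placebo mixes the two parts: about 38 of 48 placebo subjects come from Part 1, whereas all 25 mg subjects come from Part 2. A baseline shift between parts would not be chance. If it were 3 points (assumed), the 25 mg imbalance would be 3 × 38/48 = 2.4 points, and 0.9 to 1.2 points would stay uncorrected with the slope errors above. Pooling causes that imbalance; the single slope only limits how much of it is removed.

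**Conclusion.** The point holds as a cheap improvement to a valid analysis. As written, one baseline slope serves six weeks. If the true slope drifts, the common slope leans towards the early weeks and part of the Week 6 baseline adjustment is lost.

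The expected cost is about 0% to 10% of the variance of the Week 6 difference in most assumed scenarios. The most extreme closed-form setting reached 16%, or 4.8 power points. All of these sizes rest on assumed SDs and correlations. The direction rests on slope drift together with variance or correlation patterns that favour the early weeks.

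**What to change.** Before Part 1 data are unblinded for the interim analysis in SAP 4.4.6.3, add a baseline UAS7-by-week interaction to the fixed effects in SAP 4.4.3, 4.4.6.1 and 4.4.6.2. Leave the rest of the model unchanged. Record the addition in SAP 4.7 as a change from Protocol 16.8.1, and use the same model at the Part 1 and final analyses.

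If Part 1 is already unblinded, keep the primary model as it is and report the interaction model as a sensitivity analysis only. SAP 4.7 would then need to name it, since it currently drops the protocol's sensitivity analyses.

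The cost is five extra parameters with about 138 evaluable subjects (27 + 34 + 34 + 43), and no new data. If the slope is truly constant, the simulated loss was under 1% of variance (ratio 0.994). The Part 1 analysis has about 102 evaluable subjects (3 × 34), and the loss there was not computed separately.

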#### ***4.4.4 Secondary Endpoint Analysis Methods***

The secondary endpoints of change from baseline to Visit 4 (Week 6) in ISS7 and HSS7 will be summarized with descriptive statistics. Descriptive statistics will be presented for observed values and changes from baseline at each analysis visit where parameters are to be derived.

